6. STUDY PROCEDURES

6.1 Sampling

6.1.1 Size of sample

No sample size calculation was derived as this is a qualitative study where we aim to maximally sample participants across the units (not depth of investigation at each unit). We will use maximum variation sampling based on the following parameters: age, ethnicity, gender for all participants, and years of experience for NHS staff.

Patients

We plan to interview 5 patients from 6 sites but recognise that flexibility needs to be maintained to ensure diversity in the participant sample.

Staff

The planned number of staff participants is 30 (5 staff from 6 sites) but we will allow flexibility within units, for example if one participant performs both selection and procurement.

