Procedure	Screening	Visit 1 – in person	Visit 1 – remotely
Eligibility assessment	X		
Informed consent		X	X*
Type of endoscopy procedure and type of endoscope	X*		
Demographic data	X	X	X
Participate in Focus Group/Interview		X	X

*patients only.

Contents

SIGNATURE PAGE	2
KEY STUDY CONTACTS	3
STUDY SUMMARY	5
STUDY FLOW CHART	6
SCHEDULE OF EVENTS	7
LIST OF ABBREVIATIONS	10
1. INTRODUCTION	11
1.1 Background	11
1.2 Justification.....	13
1.3 Proposed study.....	14
1.4 Study population.....	14
2 OBJECTIVES.....	14
2.1 Primary objective	14
2.2 Primary outcome measures.....	14
3 STUDY DESIGN AND METHODS OF DATA COLLECTION AND ANALYSIS	14
3.1 Study Design and Data Collection	14
3.2 Data Analysis	16
4. STUDY SETTING.....	17
5. ELIGIBILITY CRITERIA	17
5.1 Inclusion criteria.....	17
5.2 Exclusion criteria	18
6. STUDY PROCEDURES.....	18
6.1 Sampling	18
6.2 Size of sample	18
6.3 Recruitment.....	18
6.4 Consent.....	19
6.5 Site Staff Training.....	19
6.6 End of study	20
7. DATA MANAGEMENT	20
7.1 Data collection and management	20
7.2 Data storage.....	21
7.3 Data access.....	21
7.4 Archiving	21

8. STUDY OVERSIGHT	21
8.1 Role and responsibilities of the Sponsor	21
8.2 Role and responsibilities of the Funder	22
8.3 Trial Management Arrangements	22
8.3.1 Trial Coordination	22
8.3.2 Principal Investigators.....	22
9. MONITORING, AUDIT & INSPECTION	22
10. ETHICAL AND REGULATORY CONSIDERATIONS.....	23
10.1 Ethical approval and research governance.....	23
10.2 Peer review	23
10.3 Public and Patient Involvement.....	23
10.4 Assessment and management of risk.....	24
11. DISSEMINATION POLICY	24
12. REFERENCES	25

LIST OF ABBREVIATIONS

CI	Chief Investigator
CRF	Case Report Form
ED&I	Equality, Diversity & Inclusion
EU	European Union
GCP	Good Clinical Practice
GI	Gastrointestinal
GP	General Practitioner
HRA	Health Research Authority
ICF	Informed Consent Form
ICH	International Council for Harmonisation of Technical Requirements for Pharmaceuticals for Human Use
ISF	Investigator Site File
NHS	National Health Service
NICE	National Institute for Health and Care Excellence
OSOP	One Sheet of Paper
PI	Principal Investigator
PIS	Participant Information Sheet
PPI	Patient and Public Involvement
PPRAG	Patient and Public Research Advisory Group
REC	Research Ethics Committee
SOP	Standard Operating Procedure
TMF	Trial Master File
TMG	Trial Management Group
UoB	University of Birmingham
UHCW	University Hospitals Coventry & Warwickshire
UoW	University of Warwick
WP	Work Package

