Robust evidence is needed to guide policy makers and practitioners to decide whether and under what circumstances single-use endoscopes may be preferred over multiple-use endoscopes. Such evidence needs to take into account clinical outcomes including infection risk, costs and environmental impact, and consider different perspectives, including those of patients and carers, healthcare staff, manufacturers and policy makers. This project aims to address this urgent need for evidence ^[11]. The work needs to be done soon before single-use endoscopes are widely implemented.

Our primary aim is to provide evidence for NHS decision makers on the use of single-use vs. multiple-use endoscopes in gastroenterology, with the following objectives and work packages (WPs):

Work package 1: Review of evidence on technical performance, test accuracy and infection risk of single-use vs multiple-use gastrointestinal (GI) endoscopes, and of literature for other work packages.

Work package 2: Assess costs and consequences arising from use of single-use endoscopes compared to multiple-use ones. It will include specific patient groups (e.g., immunocompromised, those with severe infections) and settings (e.g., intensive care unit) taking into account all factors - costs of purchase, decontamination, consequences of infections and so on.

Work package 3: Assess the wider environmental consequences of a shift to single-use endoscopes including impact on scarce resources for their production and effect of disposal, including landfill and incineration, and the greenhouse gases and waste generated (including transport and storage).

Work package 4: Explore the views of patients receiving endoscopy and staff involved in using, cleaning and decontaminating endoscopes.

Work package 5: Provide evidence for patients, health professionals, service commissioners, manufacturers, environmental management and policy makers to make decisions on single-use and multiple-use endoscopes.

The figure below explains how the WP's come together to form the mixed methods study:

[figure not shown]

Figure 1: Overview of SUMU Endo project structure

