6.2 Recruitment

Patients

We will conduct interviews with patients from 6 hospitals. The PI and research team at each site will identify potential participants through the clinic list. Potential participants who require an endoscopy will be asked if they are interested in the study and given study documentation in person. Alternatively, patients can be sent an invitation letter, PIS and consent form via post and be given at least 24 hours to decide if they would like to take part.

Interested patients can contact the research team using the details provided in the study documents. Alternatively, they will be contacted after a reasonable amount of time has passed with no response to see if they are interested. If they agree to take part, consent will be obtained either in-person at attendance of the clinic, or via the telephone if necessary.

Staff

The PI and research team at each site will generate a list of all staff who work across the endoscopy pathway and identify potential study participants. Participants will be invited to take part in the study via email invitation along with the PIS from the site PI, or informed about the study in person and given a PIS.

Staff will have at least 24 hours to decide if they'd like to take part. If they agree, the PI and research team at site will then contact the member of staff to consent them in-person. Their contact details will be provided to the experienced qualitative researcher after consent who will then organise a focus group consisting of 2-5 members of staff on Microsoft Teams. However if this is not possible, an individual interview will be scheduled. Staff recruitment will continue until all segments of the extended endoscopy care pathway are accounted for, or when saturation is reached in the data collection.

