7.1 Data collection and management

Telephone interviews will be audio recorded using encrypted devices from University of Warwick or University of Birmingham. Interviews and focus groups conducted virtually will be audio/video recorded using MS Teams or audio recorded using encrypted devices – participants can choose to turn off their camera if they wish. If not, the audio recording and transcript will be separated from the video, which will subsequently be deleted. Following the data collection, data will be pseudonymised and sent to an approved UoW/UoB supplier for transcription services, after which it will be anonymised.

Demographic data will be collected for each participant, including the age group, sex, ethnicity for all participants. For NHS patients, the type of endoscopy procedure will be

collected as well as the type of endoscope. Years of experience will be collected for NHS staff. This will be stored in a secure password protected file and kept separately to any identifiable information, identified only by unique study ID. This data will be shared with university researchers according to the terms of the Data Sharing Agreement.

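### The patient sampling parameters omit endoscope type and procedure type, so the 30 patients may include few or none with single-use experience; staff role should also be listed and recorded.

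*Protocol*

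**What the plan says.** Section 6.1.1 gives the sampling rule for both groups: "We will use maximum variation sampling based on the following parameters: age, ethnicity, gender for all participants, and years of experience for NHS staff". The planned numbers follow in the same section: "We plan to interview 5 patients from 6 sites" and "The planned number of staff participants is 30 (5 staff from 6 sites".

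Endoscope and procedure type appear elsewhere as data items only. Table 1 has a row "Type of endoscopy procedure and type of endoscope", marked at screening and for patients only. Section 7.1 says that for patients the procedure type is to be "collected as well as the type of endoscope. Years of experience will be collected for NHS staff". No section uses either item to choose patients.

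Section 4 lets any hospital in that provides endoscopy, and describes the wanted variation between participants by demographic examples. On uptake, section 1.1 says only: "The work needs to be done soon before single-use endoscopes are widely implemented".

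For staff, section 6.2 has each site list everyone along the pathway and recruit "until all segments of the extended endoscopy care pathway are accounted for", or until saturation. Section 6.1.1 allows flexible staff numbers, "for example if one participant performs both selection and procurement".

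**The concern.** Maximum variation sampling secures spread on the attributes that are named and on no others. Section 2.2 says this study is to contribute to evidence on single-use against multiple-use scopes, and section 1.2 wants to learn what would make patients content with different scope options. Yet the attribute that separates those options is recorded and plays no part in selection.

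If single-use scopes are uncommon, a sample that is well balanced on age, ethnicity and gender can still consist wholly of patients examined with multiple-use scopes. What patients then say about single-use scopes would be opinion about something they have not had, and the protocol does not say that this would be acceptable or how it would be reported. The gap is easy to close before recruitment and cannot be closed once the interviews are done.

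For staff the issue is smaller. Coverage of pathway segments is an aim, but role is neither a listed parameter nor a named data item, so the final report would lack a recorded variable with which to show that coverage.

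**Working it through.** **Planned size.** 5 patients × 6 sites = 30, and 5 staff × 6 sites = 30. Both agree with the study summary.

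**Inputs for the patient check.** n = 30 comes from section 6.1.1. The share p of eligible patients examined with a single-use scope is not in the protocol. It is assumed here over a range, with 2%, 5% and 10% as the main values. Patients are treated as independent and selection as unrelated to scope type, because no listed parameter refers to it.

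**Formulas.**
- P(none of 30) = (1 − p)^30.
- P(fewer than 3) = the sum over k = 0, 1, 2 of C(30, k) p^k (1 − p)^(30 − k).
- Number needed for a 95% chance of at least one = ln(0.05) / ln(1 − p), rounded up.

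| Assumed share p | P(none of 30) | P(fewer than 3) | Patients for 95% chance of at least one |
|---|---|---|---|
| 1% | 0.99^30 = 0.740 | 0.997 | 299 |
| 2% | 0.98^30 = 0.545 | 0.978 | 149 |
| 5% | 0.95^30 = 0.215 | 0.812 | 59 |
| 10% | 0.90^30 = 0.042 | 0.411 | 29 |
| 20% | 0.80^30 = 0.001 | 0.044 | 14 |

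**Break-even.** P(none) falls below 5% only when p exceeds 1 − 0.05^(1/30) = 0.095, that is about 9.5%.

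The last column shows scale only. Nobody would enlarge a qualitative sample for this reason; the efficient remedy is to select on the attribute.

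**Staff, by comparing sections.** Section 6.2 steers recruitment by pathway segment, and section 6.1.1 discusses staff numbers by function. The parameter list in 6.1.1 names only years of experience beyond demographics, and 7.1 names the same item as the one staff-specific variable. The wording of 7.1 leaves its list open, so role is not ruled out, but nothing commits the study to recording it. Because recruitment may also end at saturation, a record of role is what would show whether any segment had been missed.

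**The case against.** The strongest reply is that patients need not have had a single-use scope. Their objective is views and experiences of endoscopy, not a comparison of patients by scope. Section 1.2 accepts that patients may not know that there are different types, and section 3.1 sets the key questions on perceived risk from reuse or disposal and on environmental impact. Much of that can be answered without single-use experience, and the comparison of the devices themselves belongs to work packages 1 to 3. This stands, and it limits how serious the point is. It does not remove it, because the objective names experiences and the protocol never says that these may cover only one type.

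Second, the probabilities rest on assumed shares and on independent selection, whereas patients are purposively sampled, about five per site. That also stands. Clustering could move the result either way: up if a few hospitals do most single-use work and none is among the six, down if one of them is.

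Third, selecting on scope type may not always be possible. Sections 1.4 and 5.1 admit patients still awaiting the procedure, whose scope may be unknown, and nothing says that the clinic list shows it. This is fair, and the fix below allows for it. Procedure type is already partly handled, by the restriction to upper GI work in 5.1 and the mix of tertiary and district hospitals in section 4.

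A reader might infer from 6.1.1 that staff roles are left to chance. The documents do not support that: the pathway-wide staff list and the segment rule in 6.2 steer recruitment by role. Nor would a missing role field defeat a planned comparison by function, since section 3.2 plans analysis by centre and then by participant group.

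**Conclusion.** The point holds in limited form. Endoscope type and procedure type are recorded for patients but not used to select them, and no site is required to use single-use scopes. Followed as written, the plan may yield few or no patients with single-use experience. The chance of none is about 55%, 21% and 4% at assumed shares of 2%, 5% and 10%. These figures assume independent selection unrelated to scope type and show scale only; the sole support in the protocol for a low share is its remark that uptake is not yet wide, which carries no number.

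For staff, the finding is only that role or segment should be listed and recorded so that the intended coverage can be documented.

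A reader might go further and conclude that the patient component fails without single-use patients. The stated objective does not support that, because hypothetical views can meet part of it. This is a worthwhile, inexpensive improvement to the sampling plan.

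**What to change.** - **Patients, section 6.1.1:** add endoscope type (single-use or multiple-use) and procedure type to the sampling parameters. Seek single-use patients at sites that use such scopes and where the type is known at selection, for example among patients who have already had the procedure.
- **If none can be recruited:** state in the protocol and the report that patient findings on single-use scopes are hypothetical views and not experience.
- **Staff, sections 6.1.1 and 7.1:** list role or pathway segment as a sampling parameter and collect it, so that the coverage aim in 6.2 can be shown to have been met.

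The planned 30 + 30 does not change. The cost is a somewhat tighter sampling grid, one extra staff field, and a check with each site on whether it uses single-use scopes and can see scope type when selecting patients.

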6.2 Recruitment

Patients

We will conduct interviews with patients from 6 hospitals. The PI and research team at each site will identify potential participants through the clinic list. Potential participants who require an endoscopy will be asked if they are interested in the study and given study documentation in person. Alternatively, patients can be sent an invitation letter, PIS and consent form via post and be given at least 24 hours to decide if they would like to take part.

Interested patients can contact the research team using the details provided in the study documents. Alternatively, they will be contacted after a reasonable amount of time has passed with no response to see if they are interested. If they agree to take part, consent will be obtained either in-person at attendance of the clinic, or via the telephone if necessary.

Staff

The PI and research team at each site will generate a list of all staff who work across the endoscopy pathway and identify potential study participants. Participants will be invited to take part in the study via email invitation along with the PIS from the site PI, or informed about the study in person and given a PIS.

Staff will have at least 24 hours to decide if they'd like to take part. If they agree, the PI and research team at site will then contact the member of staff to consent them in-person. Their contact details will be provided to the experienced qualitative researcher after consent who will then organise a focus group consisting of 2-5 members of staff on Microsoft Teams. However if this is not possible, an individual interview will be scheduled. Staff recruitment will continue until all segments of the extended endoscopy care pathway are accounted for, or when saturation is reached in the data collection.

6.3 Consent

Patients

Written consent will be obtained prior to interview by an appropriately trained and delegated member of the research team at each site. Telephone consent will only be obtained if the patient has already attended an endoscopy appointment and has no further appointments scheduled.

In person consent: If the patient has expressed an interest to take part in the study, consent will be obtained in person at the next clinic appointment.

Telephone consent: For patients who have already had their endoscopy, consent will be obtained via telephone. A member of the research team will confirm with the patient that they have read the PIS and consent form, and answer any questions. They will go through each clause of the consent form and document on the ICF by initialling each relevant box. They will then sign the consent form in place of the participant. The process must also be documented in the patient's medical notes including the study name, start and end time of the conversation, and specify which clauses of the consent they agree/disagree to.

Staff

If they have agreed to take part, staff will be consented in person at the site by the PI or member of the research team.

It will be explained to both sets that entry into the study is entirely voluntary and the right of a participant to refuse participation without giving reasons will be respected and recorded on the screening log. Participants can withdraw prior to, during or after the interview/focus group. They will have 7 days post-interview/focus group to withdraw their data from the study, before it is anonymised. Participants may be withdrawn from the study at the discretion of the investigator and/or co-investigators due to safety concerns. However, this is not anticipated to be an issue.

6.4 Site Staff Training

The research team will provide training for all site members who will be responsible for conducting study related procedures. This will include information on confirming eligibility and obtaining consent. Training logs and the delegation log will be used to document who has received training; research staff taking part in the study will sign the site delegation log and update the study team when a new member joins the research team or the local PI changes.

6.5 End of study

The study will end after data saturation has been achieved.

The study will be stopped early if:

- Mandated by the Ethics Committee
- Funding for the study ceases

Given this study is low risk it is highly unlikely that a safety concern would emerge that would result in early termination of the study.

The REC will be notified in writing within 90 days when the study has been concluded or within 15 days if terminated early.

7. DATA MANAGEMENT

Personal data collected during the study will be handled and stored in accordance with the 2018 Data Protection Act and General Data Protection Regulation. UoW and UoB will be the data processors for this study and will store and analyse all data on secure university computers.

Personal identifying information will be held securely in password protected files on site servers. Personal data (participants name and telephone number) will be made available to members of the research team who will be responsible for undertaking the interviews/focus groups. Handling of personal data will be clearly documented in the patient information sheet and consent obtained. Personal data will be kept for up to 12 months after the study has ended.

Study data will be securely stored for up to 10 years after the study ends. Following the interviews/focus groups, data will be pseudonymised and a unique study number designated to each participant. After 7 days after the interviews/focus groups, the interview data will be anonymised.

Disclosure of confidential information will only be considered if there is an issue, which may jeopardise the safety of the participant or another person, according to UHCW SOP and the UK regulatory framework.

7.1 Data collection and management

Telephone interviews will be audio recorded using encrypted devices from University of Warwick or University of Birmingham. Interviews and focus groups conducted virtually will be audio/video recorded using MS Teams or audio recorded using encrypted devices – participants can choose to turn off their camera if they wish. If not, the audio recording and transcript will be separated from the video, which will subsequently be deleted. Following the data collection, data will be pseudonymised and sent to an approved UoW/UoB supplier for transcription services, after which it will be anonymised.

Demographic data will be collected for each participant, including the age group, sex, ethnicity for all participants. For NHS patients, the type of endoscopy procedure will be

collected as well as the type of endoscope. Years of experience will be collected for NHS staff. This will be stored in a secure password protected file and kept separately to any identifiable information, identified only by unique study ID. This data will be shared with university researchers according to the terms of the Data Sharing Agreement.

7.2 Data storage

The pseudonymised research data will be stored on secure university servers in password protected files until analysis is completed. Once complete, aggregate data will be available to write the final study reports. Identifiable participant data (email addresses and phone numbers) will be kept on a password protected file on secure university computers. This will be stored separately to raw pseudonymised research data.

7.3 Data access

All data collected will be pseudonymised after the collection of data for each participant. Confidentiality will be strictly maintained, and names or addresses will not be disclosed to anyone other than the staff involved in running the study.

Direct access to source data/documents will be available for study-related monitoring or audit by UHCW for internal audit, regulatory authorities or ethics committees.

The PI must arrange for retention of study records on site in accordance with GCP and local Trust's policies.

The CI and study team will have access to the final study data set. Contractual agreements will be in place to limit access of the final data set.

